#### 9.1.1. Adverse Events Leading to Withdrawal

A summary of incidence rates (frequencies and percentages) of TEAEs leading to treatment discontinuation, by treatment group, SOC, and PT will be provided for the Safety Population.

A data listing of AEs leading to study drug discontinuation will also be provided, displaying details of the event(s) captured on the CRF.

#### 9.1.2. Deaths and Serious Adverse Events

Any deaths that occur during the study will be listed.

Serious adverse events will be listed and also tabulated by SOC and PT and presented by treatment.

[figure not shown]
#### 9.2. Clinical Laboratory Evaluations

#### 9.2.1. Protocol-Required Safety Laboratory Tests

Hematology testing will include erythrocyte (red blood cell count), erythrocyte mean corpuscular hemoglobin concentration (MCHC), erythrocyte mean corpuscular volume (MCV), hematocrit, hemoglobin, and absolute counts of leukocytes, lymphocytes, monocytes, neutrophils, basophils, eosinophils, and platelets. Coagulation testing (prothrombin time [PT/INR]) will be performed at screening and Day 154 only.

Serum chemistry analyses will include glucose, calcium, albumin, protein, sodium, potassium, bicarbonate, chloride, magnesium, fractional calcium excretion, blood urea nitrogen (BUN), creatinine, creatine kinase, alkaline phosphatase, Alanine Aminotransferase (ALT), Aspartate Aminotransferase (AST), bilirubin, lipase, lactate dehydrogenase (LDH), and phosphate.

Urinalysis will include osmolality, creatinine, calcium, erythrocytes, leukocytes, sodium, specific

gravity, pH, specimen appearance (turbidity), color, protein, glucose, ketones, bilirubin, hemoglobin, urobilinogen, nitrite, and microscopic particles. Trace protein will be considered positive. Urine samples that did not have preservative added prior to lab analysis will be listed only.

All summaries of laboratory values from local and central lab will be presented using SI units. Observed hematology, chemistry, and urinalysis values and changes from baseline at each visit will be summarized by treatment received. Shifts from baseline regarding low/normal/high values will also be summarized by treatment received.

Shift tables summarizing the most extreme post-baseline shift for each participant within each lab parameter will be presented, with low and high results considered more extreme than normal. If a participant has both a low and high post-baseline result within a parameter, they will be counted within both the low and high rows.

The incidence of post-baseline ALT values  $\ge 3xULN$ , AST values  $\ge 3xULN$ , and AST or ALT values  $\ge 3xULN$  will be summarized.

All chemistry, hematology, and urinalysis data will be listed.

Screening laboratory tests such as viral serology, thyroid stimulating hormone, follicle-stimulating hormone, HbA1c, Folate, B12, and urine pregnancy test results will be listed only.

#### 9.3. Vital Signs

Descriptive summaries of actual values and changes from baseline will be calculated for systolic blood pressure (SBP [mmHg]), diastolic blood pressure (DBP [mmHg]), heart rate (beats/min), respiration rate (breaths/min), body temperature (C), weight (kg), and body mass index (kg/m2) by visit and treatment group.

All vital sign results will be listed.

#### 9.4. Electrocardiograms

[figure not shown]
Descriptive summaries will be presented for ECG measures of PR interval (msec), RR interval (msec), QRS interval (msec), QT interval (msec), QTc interval (both Fredericia's and Bazett's correction methods), and HR. These summaries will be presented by visit and treatment group.

The frequency and percentage of participants with normal, clinically significant abnormal, and not clinically significant abnormal ECG results will be summarized for the Safety Population by treatment group and visit.

All ECG results will be listed.

#### 9.5. Physical Examination

Frequencies and percentages of participants with normal, clinically significant abnormal, and not clinically significant abnormal physical exam findings will be summarized within the following body systems: general appearance, eyes, oral mucosa, heart, lungs, abdomen (liver/spleen), kidneys, neurological, and other. The following visits will be included:

Baseline, Day 3 (Visit 3), Day 7 (Visit 4), Day 14 (Visit 5), Day 21 (Visit 6), Day 28 (Visit 7), Day 42 (Visit 8), Day 56 (Visit 9), Day 70 (Visit 10), Day 98 (Visit 11), Day 126 (Visit 12), Day 154 (Visit 13).

All physical exam results will be listed.

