13.1.2 Physical Examination

At study visits in which a complete physical examination is required, the investigator should perform a thorough examination of all body systems (exception: genitourinary and reproductive should be symptom-directed). At study visits in which a brief physical examination is required, the investigator should inquire about signs/symptoms, general appearance, eyes (pupillary reaction, ophthalmoscopy, eye movements), oral mucosa, heart and pulses, lungs, abdomen (liver/spleen), kidneys, and neurological (symptom-directed and may include mental state, speech, gait/posture, arm swinging, facial movements, tongue, muscle wasting (power and tone), coordination, reflexes, and sensation).

Height should be measured at Screening. Weight should be measured on the same scale at each visit. The Investigator must ensure that the scale is properly calibrated prior to study initiation.

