#### 2.2. Study Endpoints

#### 2.2.1. Safety Endpoints

The safety endpoints of this study include the following:

- The incidence and severity of adverse events (AEs).
- The change in usage of concomitant medications.
- Changes in vital signs.
- Changes in physical exam findings.
- Changes in electrocardiogram findings.
- Changes in clinical laboratory testing (serum chemistry, hematology, urinalysis).
- Changes in the Columbia Suicide Severity Rating Scale (C-SSRS).

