#### **Endpoints:**

Composite endpoints based on the above categories are defined below:

- Suicidal **ideation**: A "yes" answer at any time during treatment to any one of the five suicidal ideation questions (Categories 1-5) on the C-SSRS.
- Suicidal **behavior**: A "yes" answer at any time during treatment to any one of the five suicidal behavior questions (Categories 6-10) on the C-SSRS.

• Suicidal **ideation or behavior**: A "yes" answer at any time during treatment to any one of the ten suicidal ideation and behavior questions (Categories 1-10) on the C-SSRS.

Baseline is defined as the most severe ideation and behavior reported in the past 6 months prior to the first dose of study drug. Suicidality data collected on the C-SSRS will be listed for all participants with at least one occurrence of suicidal ideation or behavior during treatment. Tables will include results from the Suicidal Ideation and Suicidal Behavior sections of the C-SSRS. Frequencies and percentages of participants with a response of "Yes" at any point as well as by study visit on the Suicidal Ideation and Suicidal Behavior items will be summarized by treatment received.

Additionally, shifts of whether participants experienced suicidal ideation, behavior, or both from pre-treatment to post-treatment will be summarized in a shift table. An additional shift table of maximum ideation from pre-treatment to post-treatment will also be provided.

All C-SSRS data will be listed.

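### The safety endpoint is change in physical examination findings, but no table planned in SAP 9.5 separates new or worsened abnormalities from pre-existing ones

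*SAP*

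**What the plan says.** Safety and tolerability are the primary objective. Protocol 6.2.1 and SAP 2.2.1 each list seven safety endpoints, and one of them in both is "Changes in physical exam findings".

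SAP 9.5 is the only place that plans an analysis of it: "Frequencies and percentages of participants with normal, clinically significant abnormal, and not clinically significant abnormal physical exam findings will be summarized" within named body systems. The visit list opens with "Baseline, Day 3 (Visit 3), Day 7 (Visit 4), Day 14 (Visit 5), Day 21 (Visit 6), Day 28 (Visit 7" and runs on to Day 154. The section closes with "All physical exam results will be listed". It mentions no shift, no change from baseline and no count of new findings.

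Other safety measures are treated differently:

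- Laboratory (SAP 9.2.1): "Shifts from baseline regarding low/normal/high values will also be summarized by treatment received", plus a table of the most extreme shift.
- Vital signs (SAP 9.3): "Descriptive summaries of actual values and changes from baseline will be calculated for systolic blood pressure" and the other measures.
- C-SSRS (SAP 9.6): a shift table for ideation and behaviour, and "An additional shift table of maximum ideation from pre-treatment to post-treatment will also be provided".

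Protocol 15.4 asks for change from baseline for laboratory measures, vital signs and ECG intervals. It is silent on the physical examination.

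**The concern.** The endpoint is worded as a change within participants, and the planned table is a series of cross-sections. A participant aged 50 to 85 who enters with a cardiac or neurological finding that persists is counted as abnormal at every visit, next to a participant whose finding appeared on treatment. The table does not tell the two apart.

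The Baseline column helps less than it seems to, because of how the examinations are scheduled. Baseline is a complete examination. Every later visit in the SAP 9.5 list is a brief one, in which Protocol 13.1.2 makes the examination "neurological (symptom-directed and may include mental state" and other elements. A finding recorded at baseline may simply not be looked for again, so a fall in the percentage abnormal need not mean improvement, and it can offset new findings in the same column.

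At stake is how readable one of seven named safety endpoints is in the study report. No decision rule depends on it.

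**Working it through.** The plan states no figure for this endpoint, so there is none to reproduce. The check has three parts.

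**1. What by-visit counts can identify.** Let n participants be examined at both baseline and a given visit, with b abnormal at baseline and v abnormal at the visit. The number newly abnormal at the visit is at least max(0, v − b) and at most min(v, n − b). Take n = 48, the planned size of one arm. The values of b and v are assumptions, because the documents give none.

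| b | v | Lower bound | Upper bound | Newly abnormal |
|---|---|---|---|---|
| 5 | 5 | max(0, 0) = 0 | min(5, 43) = 5 | 0 to 5 |
| 5 | 8 | max(0, 3) = 3 | min(8, 43) = 8 | 3 to 8 |
| 10 | 10 | max(0, 0) = 0 | min(10, 38) = 10 | 0 to 10 |
| 10 | 6 | max(0, −4) = 0 | min(6, 38) = 6 | 0 to 6 |

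Identical columns are compatible with no new abnormality or with complete turnover. A falling count (10 to 6) is compatible with six new ones.

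**2. How far carry-over can mask a difference between arms.** Suppose every baseline abnormality persists, with prevalence p at baseline in both arms, and a proportion i of those normal at baseline become abnormal. The visit percentage is then p + (1 − p)i, and a difference between arms in i shrinks by the factor 1 − p. With assumed rates of 20% on CT1812 and 5% on placebo (15 points):

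- p = 5%: 0.05 + 0.95 × 0.20 = 24% against 0.05 + 0.95 × 0.05 = 9.75%, a difference of 14.25 points.
- p = 20%: 0.20 + 0.80 × 0.20 = 36% against 0.20 + 0.80 × 0.05 = 24%, a difference of 12 points.
- p = 40%: 0.40 + 0.60 × 0.20 = 52% against 0.40 + 0.60 × 0.05 = 43%, a difference of 9 points.

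The masking is slight when few participants are abnormal at entry and material when many are. The documents do not say which applies.

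**3. Whether the columns compare like with like.**

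- Denominators: SAP 4.1 bases by-visit percentages on participants with data at that visit. Part C skips Days 3 and 21, and Parts A and B together are the first 62 participants. With 144 randomised, those two columns can therefore cover at most 62 people, and 144 − 62 = 82 are absent by design.
- Depth of examination: SAP Table 1 schedules a complete examination at screening, baseline and Day 182, and a brief one at the clinic visits from Day 3 to Day 154.
- Visits tabulated: SAP 9.5 ends at Day 154. The one complete post-baseline examination (Protocol 10.2.14) is not in the list, so no post-baseline column matches Baseline in depth.

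**The case against.** The case for leaving SAP 9.5 alone has real substance.

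- Baseline is in the table and allocation is randomised 1:1:1, so each arm's change in prevalence can be read off. This stands at group level, subject to the limits shown in part 3 of the working.
- Every result is listed by participant, so a reader can follow each person from baseline. This stands too. A reader might infer that new findings are beyond recovery or that the endpoint goes wholly unassessed, and the documents do not support that. The gap is in the tables, not in the data.
- A new unfavourable sign can qualify as an adverse event (Protocol 13.2.1), and SAP 9.1 tabulates events starting on or after the first dose. This is partial cover. Protocol 13.2.1 says that clinically significant laboratory abnormalities count as adverse events, but neither document says so of examination findings, and changes judged not clinically significant may never be reported as events.
- SAP 9.4 gives the ECG categories by visit without a shift, so the format is not unique to the physical examination, and Protocol 15.4 prescribes no analysis that SAP 9.5 breaks. Both are true. The mismatch is with the endpoint's own wording.
- Participants must be generally healthy, many diseases are excluded, and SAP 9.5 keeps the two abnormal categories apart. Prevalence per body system may therefore be low, and stable minor findings would not blur the clinically significant row. This limits the likely size of the masking.

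A reader might also infer that the trial loses power. It does not. No test of examination findings is planned, so power is not a property of this analysis. Any such figure would rest on invented rates and very few events: with 40% abnormal at entry, 48 × 0.60 = 28.8 placebo participants at risk and 28.8 × 0.05 = 1.4 expected events.

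**Conclusion.** The point holds as a reporting gap in the planned tables. An endpoint defined as change is tabulated only as by-visit prevalence. No planned table isolates new or worsened abnormalities; the listing does so participant by participant, and the treatment-emergent adverse event tables do so in part.

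That the counts do not identify new onset follows from the bounds and needs no assumption beyond some participants being abnormal at baseline. How much this matters in practice depends on baseline prevalence and on how consistently old findings are re-recorded, and the documents give neither. The 14.25-point and 9-point differences above are illustrations under assumed rates and full persistence, not estimates for this trial.

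The gap is modest, with no effect on sample size, alpha or efficacy. It is still worth closing, because the endpoint serves the primary objective, the SAP already uses this method for other safety measures, and the remedy is nearly free.

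**What to change.** In SAP 9.5:

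1. Add a descriptive shift table by body system and treatment group (100 mg, 300 mg, pooled CT1812, placebo) from baseline category to worst post-baseline category.
2. With it, give the number and percentage newly abnormal or worsened, among participants examined at baseline and at least once afterwards. State the order of the three categories, from normal through abnormal but not clinically significant to clinically significant.
3. Add the Day 182 complete examination to the visit list, and show the shift from baseline to Day 182 as well. Both are complete examinations, so this shift is free of the complete-versus-brief mismatch that remains in the worst-post-baseline table.
4. State whether early-termination examinations count towards the worst category, since SAP 6.1.6 keeps those before Day 170 to the listing.
5. Keep the by-visit table.

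The cost is one or two further descriptive tables from data already collected, with no new assessments and no test.

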10.2.11 Participant Study Day 90, Serum Collection

 Collect serum sample on Day 90 (+/- 2 days) (see Section 11.2 for details and the laboratory manual).

participant

10.2.12 Visits 11, 12 and 13 / Study Days 98, 126 and 154

- Perform cognitive testing Day 98 only (see Section 12.1 for details).
- Perform MMSE Day 98 only.
- If a participant and investigator are agreeable, an additional LP may be performed at least 24 hours before the Day 98 visit (see Section 11.5 for details).
- Perform brief physical examination (see Section 13.1.2 for details).
- Measure and record vital signs (see Section 13.1.3 for details).
- Draw blood and prepare sample for serum chemistry and hematology (see Section 13.1.4 for details).
- Draw blood for coagulation testing Day 154 only (see Section 13.1.4 for details).
- Draw blood and prepare sample for serum cystatin C (see Section 13.1.5.1 for details).

- Collect blood samples for PK and exploratory biomarker analysis (see Section 11.2 for timing of sample collection).
- Collect urine samples for urinalysis (see Section 13.1.4 for details).
- Administer C-SSRS Since Last Visit version (see Section 13.1.6).
- Drug dispensation.
- Administer dose with or without food.
- Record any AEs.
- Record changes in medications.
- Conduct drug accountability on returned bottle.

- Record 12-lead ECG Day 98 only, approximately 2 hours post-dose (see Section 13.1.7 for details).
- On Day 154, Visit 13 instruct participant to go to a local lab at Day 172 for serum collection.

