10.2.13 Participant Study Day 172, Serum Collection

Collect serum sample on Day 172 (+/- 2 days) (see Section 11.2 for details and the laboratory manual).

10.2.14 Participant Visit 14 / Study Day 182, End of Study Treatment Early Termination

This visit should be used as the Early Termination visit should the participant discontinue the study earlier than the Study Day 210 visit.

The participant will return to the clinic.

- Perform cognitive testing (see Section 12.1 for details).
- Perform MMSE.

- Perform complete physical examination (see Section 13.1.2 for details).
- Measure and record vital signs (see Section 13.1.3 for details).
- Draw blood and prepare sample for serum chemistry and hematology (see Section 13.1.4 for details).
- Draw blood and prepare sample for serum cystatin C (see Section 13.1.5.1 for details).
- Collect blood samples for PK and exploratory biomarker analysis (see Section 11.2 for timing of sample collection).
- Collect urine samples for urinalysis (see Section 13.1.4 for details).
- Optional: Perform lumbar puncture pre-dose (note: lumbar puncture may be performed pre-dose on Day 178, 179, 180 or 181 for ease of scheduling) (see Section 11.5 for details).
- Administer C-SSRS Since Last Visit version (see Section 13.1.6).
- Record any AEs.
- Record changes in medications.
- Conduct drug accountability on returned bottle.
- Administer Day 182 dose with or without food.

- Perform 12-lead ECG ~ 2 hours post-dose (see Section 13.1.7 for details).
- Perform MRI.

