10.2.15 Study Day 210 – Safety Follow-up Visit

Measure and record vital signs (see Section 13.1.3 for details).

- Draw blood and prepare sample for serum chemistry and hematology (see Section 13.1.4 for details).
- Draw blood and prepare sample for serum cystatin C (see Section 13.1.5.1 for details).
- Administer C-SSRS Since Last Visit version (see Section 13.1.7).
- Record any AEs.
- Record changes in medications.

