- 9. Screening labs include viral serology, Thyroid-stimulating hormone (TSH), Folliele-stimulating hormone (FSH) and Hemoglobin A1c (HbA1c).
- 10. Complete physical examination = thorough examination of all body systems, including height, weight, and neurological exam. Weight should be measured on the same scale each time. Height measured only at screening.

AD-ST-33.05 Effective date: 22-Jan-2018

Version Final 2.0 | 23May2024 Page 13 of 37

Statistical Analysis Plan, Sponsor Cognition Therapeutics, Inc. Protocol Number COG0201 PCN Number COGN187880

[figure not shown]

- 11. Brief physical examination = inquire about signs/symptoms, review of general appearance and brief review of body systems, including weight. Weight should be measured on the same scale each time.
- 12. Vital signs will include body temperature, systolic and diastolic BP, respiration rate and pulse rate. Weight should also be recorded. At Baseline and subsequent visits, vital signs are done at pre-dose.
- 13. ECG to be conducted during screening period, and approximately two hours post-dose (+/- 45 min) at specified visits.
- 14. MRI (or CT scan due to contraindication of MRI if approved by medical monitor) performed at screen (if an historical MRI is not used) and end of treatment.
- 15. Diagnostic confirmation by amyloid PET with florbetaben or another approved amyloid PET ligand. Diagnostic confirmation by cerebrospinal fluid (CSF) sample collected at Screen Lumbar Puncture, in place of the amyloid PET, will also be accepted.
- 16. Blood Chemistry and Hematology Blood should be drawn within an hour of urine collection.
- 17. Serum cystatin C: Blood should be drawn within an hour of urine collection.
- 18. Plasma PK and Exploratory Biomarker Sampling: See Laboratory Procedures Manual for sample handling. PK will not be assessed at screen whereas the exploratory biomarker samples will be collected.

  Serum biomarker samples are collected at any point during screening at least 24 hours prior to the Baseline Visit. Serum biomarkers will also be collected.
  - Serum biomarker samples are collected at any point during screening at least 24 hours prior to the Baseline Visit. Serum biomarkers will also be collected at Day 90 (+/- 2 days) and Day 172 (+/- 2 days).

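### The by-arm physical-examination summary in SAP 9.5 stops at Day 154 and omits Day 182, the end-of-treatment visit and the only complete examination scheduled after baseline

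*SAP*

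**What the plan says.** SAP 2.2.1 makes physical examination a safety endpoint in terms of change: "Changes in physical exam findings". SAP 9.5 plans frequencies and percentages of normal, clinically significant abnormal and not clinically significant abnormal findings by body system. The opening of SAP Section 9 has all safety analyses presented by actual treatment received.

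SAP 9.5 introduces its visits with "The following visits will be included". The list starts "Baseline, Day 3 (Visit 3), Day 7 (Visit 4), Day 14 (Visit 5), Day 21 (Visit 6") and ends "Day 98 (Visit 11), Day 126 (Visit 12), Day 154 (Visit 13"). A sentence then says that all physical-examination results will be listed.

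For Day 182, Protocol 10.2.14 has the entry "Perform complete physical examination (see Section 13.1.2 for details"). For Days 98, 126 and 154, Protocol 10.2.12 has "Perform brief physical examination (see Section 13.1.2 for details"). The SAP Table 1 notes define the fuller version: "Complete physical examination = thorough examination of all body systems, including height, weight, and neurological exam".

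SAP 6.1.6 sets the general rule for Visit 14. Day 182 data enter the summary tables only if they occur after study Day 170. Termination visits before then are listed only.

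**The concern.** The visit list in SAP 9.5 is closed: it has no wording such as for example, and no catch-all for other visits. A programmer following it would produce a table without the end-of-treatment examination. Safety and tolerability is the primary objective, and Day 182 closes the dosing period. It is also the one post-baseline visit where the scheduled examination is of the same type as at baseline. At stake is the by-arm display of physical findings after the full course of treatment. A listing does not give that display, because it has no frequencies or percentages by arm.

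**Working it through.** The plan gives no figure to reproduce. The check sets the SAP 9.5 list against the examination rows of SAP Table 1 and Protocol Table 1, and against Protocol 10.2.2 to 10.2.15.

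| Visit | Examination scheduled | In SAP 9.5 list |
|---|---|---|
| Day 1 (baseline) | complete | yes |
| Days 3 and 21 (Parts A and B only) | brief | yes |
| Days 7, 14, 28, 42, 56, 70, 98, 126, 154 | brief | yes |
| Day 182 (Visit 14) | complete | **no** |
| Day 210 | none | no |

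The last row rests on the procedures under "Study Day 210 – Safety Follow-up Visit" in the protocol, which include no physical examination. Its absence from SAP 9.5 is therefore correct.

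**Counts**

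- Parts A and B: 2 + 9 + 1 = 12 post-baseline examination visits. SAP 9.5 tabulates 11 and omits 1.
- Part C, without Days 3 and 21: 9 + 1 = 10. SAP 9.5 tabulates 9 and omits 1.
- Complete post-baseline examinations: 1 scheduled, 0 tabulated.
- Time on treatment: the last tabulated visit is at 154/182 = 84.6% of the period, so the final 182 − 154 = 28 days are not represented in this table.

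**Participants touched.** With the planned maximum of 48 per arm, and borrowing the 15% dropout assumed for the ADAS-Cog 11 power statement, 48 × 0.85 = 40.8, or about 41 per arm. This counts people with a Day 182 examination, not people with a finding, so it does not measure lost information.

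**Consistency within the SAP**

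- SAP 6.1.6 presupposes that Day 182 data are tabulated, subject to the Day 170 cut.
- SAP 9.2 summarises laboratory values at each visit, and SAP 9.3 and 9.4 summarise vital signs and ECGs by visit. None of them excludes Day 182. SAP 9.5 is the only one of these sections whose stated list cuts it off.
- The document history says that V2.0 added the visits to be summarised in Section 9, including 9.5, so the list is current text.
- SAP Section 10 does not mention leaving out Day 182.

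**The case against.** The best case on the other side is that little is lost, and most of it stands.

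- **The data remain available.** All examination results are listed. An adverse event under Protocol 13.2.1 includes any unfavourable and unintended sign, so a finding of concern at Day 182 can enter the treatment-emergent tables by arm. The SAP definition of treatment-emergent has no end date.
- **Other safety data at Day 182 are compared by arm.** Laboratory values, vital signs, weight and ECGs all are. A reader might infer that the plan makes no by-arm safety comparison at full exposure. The documents do not support that; the gap is confined to this one table.
- **The brief examinations are not useless against baseline.** A reader might also infer that Day 182 is the only examination that can be compared with baseline. That goes too far. The eight named body-system categories in SAP 9.5 all appear in the brief examination of Protocol 13.1.2, although its neurological part is symptom-directed. Systems examined only in the complete version have no row of their own and would fall under the category for other findings.

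Three things are left after these concessions. A listing does not replace by-arm frequencies. Adverse event tables would not be expected to carry abnormalities judged not clinically significant, which SAP 9.5 sets out to count. Nor can it be said that a complete examination does not fit the table, because baseline is a complete examination and is in the list.

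**Conclusion.** SAP 9.5 is wrong as written, with minor severity. It omits one scheduled examination visit (1 of 12 in Parts A and B, 1 of 10 in Part C), which is the end-of-treatment visit and the only complete examination scheduled after baseline. The omission conflicts with SAP 6.1.6 and is unexplained. The endpoint on change in physical findings therefore has no by-arm tabulation at end of treatment.

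The table is descriptive and carries no test or decision rule. The efficacy analysis, alpha and sample size do not change.

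The conclusion assumes that the specific list in 9.5 governs over the general rule in 6.1.6. If the programmers apply 6.1.6 and add Day 182 anyway, the output is right but departs from the list. A deliberate choice to leave Day 182 out should not be inferred: the documents give no reason for it, and 6.1.6 points the other way, so a drafting slip is the more natural explanation.

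**What to change.** Add Day 182 (Visit 14) to the visit list in SAP 9.5 and state that the 6.1.6 rule applies: visits after study Day 170 are tabulated, and earlier termination visits are listed only. Do not label the entry as Day 182 or early termination without that rule. Both share one label in the data capture system, so such a label would mix early-termination examinations into the Day 182 results, against 6.1.6. If leaving Day 182 out was intended, say so and give the reason in SAP Section 10.

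The cost is one more visit in an existing table. No new data collection and no protocol change are needed.
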